10.2 Pharmacodynamics

10.2.1 Total serum IgG and IgG subclasses

Total serum IgG concentrations and IgG subclasses will be summarized by first dose received and time point for observed values, change from Baseline, and percentage change from Baseline.

The maximum change from Baseline in total serum IgG (absolute and percentage change) will be reported in the listing and summarized by first dose received. In the event that a change from Baseline in total serum IgG is not observed in a given participant, the maximum change will be reported as the smallest increase from Baseline.

Mean and mean percentage change from Baseline values in total serum IgG will be plotted over time by first dose received with dose groups overlaid on the same plot.

Spaghetti plots will be provided for absolute IgG and percentage change from baseline in IgG over time stratified by first dose received and Baseline bodyweight group (<50kg, 50kg-<70 kg, 70-<100kg, ≥100kg) where the Baseline bodyweight group is multipaneled or overlaying with different colors within each treatment group.

Serum concentrations of total IgG and IgG subclasses will be listed together with concentrations of rozanolixizumab, ADA and NAb sample status and titer, MG-specific autoantibodies, and MG-ADL change from Baseline, as specified in [Section 10.3.2](#).

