To assess the pharmacodynamic effects of rozanolixizumab as measured by IgG levels, IgG subclasses, and MG-specific autoantibodies levels	
 • Change from baseline in total IgG and IgG subclasses autoantibodies at each scheduled visit • Change from baseline in MG-specific autoantibodies at each scheduled visit
To evaluate the incidence and emergence of ADAs with respect to immunogenicity, PK, and pharmacodynamics	
 • ADAs at each scheduled assessment during the Treatment Period and Observation Periods
To assess the effect of rozanolixizumab on biomarkers including IgM, IgA, and IgE, serum and plasma complement levels, and serum cytokines	
 • Change from Baseline in serum complement levels (C3 and C4) and plasma complement levels (C3a and C5a) at each scheduled assessment during Treatment Period^a • Change from Baseline in serum cytokines at each scheduled assessment during Treatment and Observation Periods^a • Change from Baseline in serum immunoglobulin concentrations (total IgA, IgE, and IgM) at each scheduled assessment during Treatment and Observation Periods
To assess the effect of rozanolixizumab on tetanus IgG antibodies	
 • Change from Baseline in anti-tetanus toxoid serum titers at each scheduled assessment during Treatment and Observation Period

ADA=anti-drug antibody; ADL=activities of daily living; AESM=adverse event of special monitoring; ECG=electrocardiogram; Ig=immunoglobulin; IVIg=intravenous infusion of immunoglobulin G; MG=myasthenia gravis; MG-ADL=myasthenia gravis-activities of daily living; MGII=myasthenia gravis impairment index; MGQoL15r=revised 15-item myasthenia gravis quality of life questionnaire; PEX=plasma exchange; PK=pharmacokinetic; PRO=patient-reported outcome; QMG=quantitative myasthenia gravis test; SC=subcutaneous(ly); TEAE=treatment-emergent adverse event

^a To be performed for study participants with severe and/or serious headache and/or infusion reaction or hypersensitivity reaction. Other exploratory safety biomarkers may be assessed.

Overall design:

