Treatments aimed at reducing the quantity of circulating IgG autoantibodies, including plasmapheresis, immunoadsorption, or high dose IVIg, are being used for primary and secondary therapy of autoimmune disease, particularly where corticosteroid based immune suppression is not or no longer effective (eg, ITP, MG, GBS, PV). The therapeutic approach of these treatments is thought in part to be based on lowering levels of pathogenic autoantibodies, which represents rational and effective treatment modalities of autoimmune diseases.

Therefore, specific removal of the IgG autoantibodies by FcRn blockade may provide an effective therapeutic option for IgG autoantibody-mediated autoimmune disorders.

More detailed information regarding the nonclinical and clinical development programs for rozanolixizumab, including all completed and ongoing studies, can be found in the latest version of the Investigator's Brochure (IB).

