To assess the pharmacodynamic effects of rozanolixizumab as measured by IgG levels, IgG subclasses, and MG-specific autoantibodies levels	
 • Change from baseline in total IgG and IgG subclasses autoantibodies at each scheduled visit • Change from baseline in MG-specific autoantibodies at each scheduled visit
To evaluate the incidence and emergence of ADAs with respect to immunogenicity, PK, and pharmacodynamics	
 • ADAs at each scheduled assessment during the Treatment Period and Observation Periods
To assess the effect of rozanolixizumab on biomarkers including IgM, IgA, and IgE, serum and plasma complement levels, and serum cytokines	
 • Change from Baseline in serum complement levels (C3 and C4) and plasma complement levels (C3a and C5a) at each scheduled assessment during Treatment Period^a • Change from Baseline in serum cytokines at each scheduled assessment during Treatment and Observation Periods^a • Change from Baseline in serum immunoglobulin concentrations (total IgA, IgE, and IgM) at each scheduled assessment during Treatment and Observation Periods
To assess the effect of rozanolixizumab on tetanus IgG antibodies	
 • Change from Baseline in anti-tetanus toxoid serum titers at each scheduled assessment during Treatment and Observation Period

ADA=anti-drug antibody; ADL=activities of daily living; AESM=adverse event of special monitoring; ECG=electrocardiogram; Ig=immunoglobulin; IVIg=intravenous infusion of immunoglobulin G; MG=myasthenia gravis; MG-ADL=myasthenia gravis-activities of daily living; MGII=myasthenia gravis impairment index; MGQoL15r=revised 15-item myasthenia gravis quality of life questionnaire; PEX=plasma exchange; PK=pharmacokinetic; PRO=patient-reported outcome; QMG=quantitative myasthenia gravis test; SC=subcutaneous(ly); TEAE=treatment-emergent adverse event

^a To be performed for study participants with severe and/or serious headache and/or infusion reaction or hypersensitivity reaction. Other exploratory safety biomarkers may be assessed.

Estimands

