6.5.3 Rescue therapy

Rescue therapy for the study will consist of IVIg or PEX. The study site will supply rescue therapy that will be obtained locally.

Study participants who experience disease worsening (eg, an increase of 2 points on the MG-ADL or 3 points on the QMG scale between 2 consecutive visits) may be considered for rescue therapy at the discretion of the Investigator.

If the study participant receives IVIg or PEX as rescue therapy during the study, treatment with rozanolixizumab should be discontinued or paused for a minimum of 2 weeks, but continue with visits as per Schedule of Activities, after which the participant may continue to receive rozanolixizumab at the discretion of the Investigator. This 2-week period may be extended at the discretion of the Investigator, but for no longer than 6 weeks. Following the temporary discontinuation of study medication, study participants should be restarted at the same dose of rozanolixizumab as previously. Study participants at a dose level of [REDACTED] rozanolixizumab can be restarted at [REDACTED] rozanolixizumab at the discretion of the Investigator.

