10.2.2 MG-specific autoantibodies

MG-specific autoantibodies (anti-MuSK/anti-AChR) will be summarized by first dose received and RLZ total at scheduled visits for observed values, absolute and percentage changes from Baseline. The maximum change from Baseline in MG-specific autoantibodies (absolute and percentage change) will be reported in the listing and summarized for each treatment.

MG-specific autoantibodies will also be summarized at scheduled visit by the participants who are anti-MuSK or anti-AChR autoantibody-positive at the Baseline visit.

Mean absolute and mean percentage change from Baseline values in MG-Specific autoantibodies will be plotted over time by treatment group and RLZ total. Additionally, mean percentage change from Baseline in anti-MuSK, total IgG, MG-ADL, QMG, and MG-C will be plotted by first dose received. The same plot will be repeated for percentage change from Baseline values in anti-AChR.

MG-specific autoantibodies will be listed, together with total IgG, MG-ADL, QMG, MG-C change from Baseline.

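### Total IgG, autoantibody and tetanus summaries mix in samples taken after rescue IVIg or plasma exchange, unflagged and with no rescue-excluded version alongside

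*SAP*

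**What the plan says.** The pharmacodynamic objective in protocol Section 3 is specific to the drug: "To assess the pharmacodynamic effects of rozanolixizumab as measured by IgG levels, IgG subclasses, and MG-specific autoantibodies levels".

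SAP 10.2.1 and 10.2.2 summarise total IgG, IgG subclasses and MG-specific autoantibodies by first dose received and visit, on the Safety Set. Both add an extreme per participant. For IgG, "The maximum change from Baseline in total serum IgG (absolute and percentage change) will be reported"; for autoantibodies, "The maximum change from Baseline in MG-specific autoantibodies (absolute and percentage change) will be reported in the listing", with a summary as well. SAP 10.4.4 summarises anti-tetanus titers by visit and plots their mean change with mean IgG change overlaid. SAP 4.3 uses the scheduled post-dose value whenever it is non-missing.

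On rescue, protocol 6.5.3 states: "Rescue therapy for the study will consist of IVIg or PEX". Afterwards "treatment with rozanolixizumab should be discontinued or paused for a minimum of 2 weeks, but continue with visits as per Schedule of Activities". The pause may be extended, "but for no longer than 6 weeks", and dosing may then resume. Footnote p to the Schedule of Activities has total IgG drawn at every scheduled site visit.

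The Estimands text in protocol Section 3 names rescue as a main intercurrent event, adopts treatment policy, and places biomarkers on the Safety Set by first dose received.

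**The concern.** Both rescues act on the quantities being summarised. The abbreviations under the objectives table read "IVIg=intravenous infusion of immunoglobulin G", so IVIg adds to what the total IgG assay measures. The protocol Introduction refers to "Treatments aimed at reducing the quantity of circulating IgG autoantibodies, including plasmapheresis, immunoadsorption, or high dose IVIg", and says such treatments are thought to work in part by lowering pathogenic autoantibodies.

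A post-rescue sample, often taken while rozanolixizumab is on hold, therefore reflects the rescue as well as the drug. Two outputs are exposed in different ways:

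- **By-visit means and plots.** IVIg can pull mean IgG change toward or above Baseline and hide drug effect. PEX can deepen it.
- **Maximum change.** The SAP fallback for a participant with no fall in IgG is the smallest increase, so the maximum means the largest decrease. A low post-PEX value can become the recorded maximum drug effect.

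A reader of the planned tables could not separate these values, because the pharmacodynamic listings as described carry no rescue indicator. The ADA outputs in SAP 10.3.2 that use IgG change draw on the same data.

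**Working it through.** The plan states no figure to reproduce: there is no sample size calculation, rescue rate or expected post-rescue level.

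**1. Is there a rule for post-rescue samples?** SAP 3.3 (Baseline), 3.5 (analysis sets), 4.2 (missing data), 4.3 (repeated measurements), 10.2 and 10.4.4 contain none. There is no separate pharmacodynamic set. Retention is thus inferred from the absence of a rule together with the treatment-policy choice; no sentence says it outright.

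**2. Will affected samples be drawn?** In Weeks 9 to 48 site visits are 4 weeks (28 days) apart. For a pause starting at a random time:

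- Total IgG, 2-week pause: 14/28 = 0.5 chance of containing a sample.
- Total IgG, 6-week pause: 42/28 = 1.5 samples on average, so 1 or 2.
- Autoantibodies (Weeks 9, 21, 33 and 45, so 84 days apart): 14/84 = 0.17 and 42/84 = 0.5.

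Tetanus titers, taken every 6 months in that span, will overlap a pause less often still.

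**3. Shift in a visit mean.** Let f be the share of participants at a visit whose value is affected by rescue, u the unrescued mean change and v the post-rescue change:

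mean = (1 - f) × u + f × v

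Take u = -70%, from protocol 4.3 (MG0002: mean nadir 3.3 g/L, about 70% below Baseline). This is a nadir in one dose group, used here for illustration. Both f and v are assumptions.

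| v (assumed) | f = 1% | f = 5% | f = 10% |
|---|---|---|---|
| IVIg, 0% | -69.3% | -66.5% | -63.0% |
| IVIg, +50% | -68.8% | -64.0% | -58.0% |
| IVIg, +100% | -68.3% | -61.5% | -53.0% |
| PEX, -85% | -70.15% | -70.75% | -71.5% |

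For example, f = 5% and v = +50%: 0.95 × (-70) + 0.05 × 50 = -66.5 + 2.5 = -64.0%.

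**4. Maximum change.** The participant's maximum is the lowest value over up to 17 post-Baseline IgG samples to Week 52. A post-PEX value sets it only if it lies below the lowest of the others. The documents give no post-PEX level, so how often this happens cannot be calculated. IVIg-raised total IgG would rarely set a maximum decrease.

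**5. What would excluding everything after rescue remove?** Total IgG has 18 post-Baseline site samples: Weeks 2, 3, 4, 5, 7, 9, then 13 to 45 every 4 weeks (9 samples), then 49, 52 and 60. For rescue at Week 10 with a 6-week pause, only Week 13 falls inside the pause. Excluding all later values removes 9 + 3 = 12 of 18, many possibly back on drug.

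**The case against.** The strongest reply is that keeping post-rescue values follows a declared strategy. Protocol Section 3 calls treatment policy the only viable option, defines intercurrent events for all variables, and names biomarkers explicitly. That stands. A reader might infer that treatment policy was meant for efficacy alone and that the pharmacodynamic data were overlooked; the text does not support this.

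The size is also uncertain. The SAP puts the maximum sample at 240. With an assumed 120 per arm, one participant at +50% moves the mean only from -70% to (119 × (-70) + 50)/120 = -69%. That stands too, although smaller cells such as the anti-MuSK-positive summaries and the bodyweight panels are more exposed.

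A reader might further infer that one post-exchange value automatically replaces the drug value as the maximum, or that all post-rescue values should leave the main tables. Step 4 rules out the first. Step 5 argues against the second: rescue follows disease worsening, so the deletion is informative, and other off-drug samples (pauses for low IgG or COVID-19, and the Observation Period) would remain anyway.

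Finally, a determined reader could trace affected values by combining the individual IgG plots, time since dosing and the rescue listings. That is possible but laborious, and it does not correct any mean.

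What the reply does not answer is the mismatch with the objective. Treatment policy suits the question of how participants fare under the regimen. It suits less well an assay that measures the rescue product. Setting aside observed samples in a descriptive table also needs none of the assumption-heavy modelling that the protocol gives as its reason for rejecting a hypothetical estimand.

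**Conclusion.** The point holds as a reporting gap. The planned summaries are consistent with the protocol's general estimand, but for these analytes they do not isolate the effect of rozanolixizumab, and nothing planned lets a reader see how far rescue has moved them.

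The bias can go either way. It is about 1 percentage point if 1% of participants at a visit are affected, and 6 to 12 points at 5% to 10%, assuming a post-IVIg level of +50% and an unrescued mean of -70%. The true size is unknown because neither the rescue rate nor post-rescue levels are given. Baseline is largely protected, since participants who received IVIg or PEX in the lead-in Observation Period cannot enter. These are descriptive endpoints listed under Other, and no test depends on them. A cheap supplementary analysis is proportionate; replacing the planned one is not.

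**What to change.** Keep the planned all-data summaries. In SAP 10.2.1, 10.2.2 and 10.4.4:

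- Add a supplementary version of the by-visit summaries and mean plots, and of maximum change for total IgG and autoantibodies. It should exclude values on or after the first IVIg or PEX in MG0004 and show the number excluded at each visit.
- Flag post-rescue values in the pharmacodynamic listings and the IgG spaghetti plots.
- Identify rescue as in SAP 6.4, which uses either the medication page or PEX on the procedure page. Align SAP 9.1.4, which names only the medication page, so that the same events are counted throughout.
- Footnote the supplementary tables to say that later-visit means describe only participants not yet rescued.

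The cost is SAP wording, one agreed rescue definition, a filter on dates already collected, and a few extra outputs. The SAP already repeats summaries on filtered data, for COVID-19-free MG-ADL and for tetanus without undetectable Baselines. The limitation is the selection named in the footnote, which is why this version should sit beside the planned one.

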10.2.2 MG-specific autoantibodies

MG-specific autoantibodies (anti-MuSK/anti-AChR) will be summarized by first dose received and RLZ total at scheduled visits for observed values, absolute and percentage changes from Baseline. The maximum change from Baseline in MG-specific autoantibodies (absolute and percentage change) will be reported in the listing and summarized for each treatment.

MG-specific autoantibodies will also be summarized at scheduled visit by the participants who are anti-MuSK or anti-AChR autoantibody-positive at the Baseline visit.

Mean absolute and mean percentage change from Baseline values in MG-Specific autoantibodies will be plotted over time by treatment group and RLZ total. Additionally, mean percentage change from Baseline in anti-MuSK, total IgG, MG-ADL, QMG, and MG-C will be plotted by first dose received. The same plot will be repeated for percentage change from Baseline values in anti-AChR.

MG-specific autoantibodies will be listed, together with total IgG, MG-ADL, QMG, MG-C change from Baseline.

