4.2 Scientific rationale for study design

The lead-in studies, MG0003 and MGC003, will evaluate the efficacy, safety, and tolerability of rozanolixizumab compared with placebo in study participants with generalized MG who are treated with study medication over a [REDACTED] at [REDACTED]. Study participants in the lead-in studies will have generalized MG, as evidenced by the presence of anti-AChR or anti-MuSK antibodies. Additionally, study participants in the lead-in studies will have moderate to severe symptoms of MG and should be under consideration for IVIg or PEX therapy, indicating that they are in need of additional therapeutic intervention.

Study participants in MG0003 or MGC003 will be randomized to receive either placebo or 1 of 2 doses of rozanolixizumab. Study participants in MG0003 or MGC003 who require rescue medication (other than IVIg or PEX) during the Observation Period will be invited to be rerandomized in MG0004: this will offer all study participants, even those previously treated with placebo, a chance to be treated with rozanolixizumab. Rerandomization in MG0004 is applied to account for the limited efficacy information on the [REDACTED] dose. Due to the open-label design of MG0004, study participants are allowed to switch dose at the Investigator's discretion during the course of the study (dose modification recommendations for safety are provided in Section 6.6). Study participants developing TEAEs could be switched to a dose equivalent to [REDACTED] and study participants experiencing symptom worsening can be switched to a dose equivalent to [REDACTED].

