8.7 Pharmacodynamics

Venous blood samples will be collected at timepoints specified in the Schedule of Activities (Section 1.3), for measurement of:

- Serum IgG and IgG sub-classes concentrations
- Serum MG-specific autoantibodies (anti-MuSK/anti-AChR) levels

For all PD assessments, blood samples will be collected predose. Instructions pertaining to sample collection, processing, storage, labeling, and shipping are provided in the laboratory manual.

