2.4 Determination of sample size

No formal sample size calculation can be performed. Up to approximately 240 study participants will be enrolled into the lead-in study MG0003. All eligible study participants from MG0003 will be invited to participate in MG0004 until study site approval of MG0007 as well as fulfilment of regulatory requirements.

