6.2 Other Baseline characteristics

The following variables will be summarized by treatment group and RLZ total for the RS. The baseline values are derived according to [Section 3.3](#).

- Baseline MuSK antibody status (positive, negative)
- Baseline AChR antibody status (positive, negative)
- Baseline MG-ADL score
- Baseline MG-ADL category (< 5 , ≥ 5)
- Baseline QMG score
- Baseline MG-C score
- Baseline total IgG value

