10 PHARMACOKINETICS AND PHARMACODYNAMICS

All PK and PD analyses described in this section will be performed by first dose received on the SS, as described in [Section 3.6](#), unless specified otherwise.

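### SAP 10.2.2: the maximum-change summary, mean-change plots and combined figures for each autoantibody default to including participants who lack that antibody, which can strongly dilute the rarer one

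*SAP*

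**What the plan says.** - **Default population.** SAP Section 10 opens with "All PK and PD analyses described in this section will be performed by first dose received on the SS", subject to exceptions stated locally.
- **Outputs in SAP 10.2.2.** After a by-visit summary of values and changes, the section states: "The maximum change from Baseline in MG-specific autoantibodies (absolute and percentage change) will be reported in the listing and summarized for each treatment". It then adds one restricted output: "MG-specific autoantibodies will also be summarized at scheduled visit by the participants who are anti-MuSK or anti-AChR autoantibody-positive at the Baseline visit". The plots follow: "Mean absolute and mean percentage change from Baseline values in MG-Specific autoantibodies will be plotted over time by treatment group and RLZ total". A further figure sets mean percentage change in anti-MuSK beside total IgG, MG-ADL, QMG and MG-C, and is repeated for anti-AChR. Neither the maximum-change summary nor any figure carries a serostatus condition.
- **Who is in the study.** Protocol 4.2 describes lead-in participants as having generalized MG "as evidenced by the presence of anti-AChR or anti-MuSK antibodies". SAP 6.2 tabulates Baseline status as positive or negative for each antibody separately. Protocol 8.7 lists "Serum MG-specific autoantibodies (anti-MuSK/anti-AChR) levels" among the samples taken, without limiting either assay by serostatus.
- **A comparable analyte.** For anti-tetanus titers, SAP 10.4.4 draws the mean-change plot without participants whose Baseline titer is undetectable. SAP 10.4.1 to 10.4.4 all set values below quantification to half the LLOQ. SAP 10.2.2 has neither provision.

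**The concern.** Someone who qualified on anti-AChR may well be negative for anti-MuSK, and the reverse. For a negative participant, a change in that antibody carries no information about the drug. It is a zero, a ratio of two values near the assay limit, or undefined. Averaging such values with those of true positives pulls the mean toward zero, and does so most for the antibody that fewer participants have.

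Change in MG-specific autoantibodies is a stated pharmacodynamic endpoint (SAP 2.2.3.2). The combined figure is the most exposed output, because a reader will take it as mechanism set beside response. As planned, its anti-MuSK curve could rest mainly on people without anti-MuSK, next to IgG and clinical curves from everyone.

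**Working it through.** There is no plan figure to reproduce: SAP 2.4 states "No formal sample size calculation can be performed", and all analyses are descriptive. The check is a mixture calculation plus a simulation of the maximum change.

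**Inputs**
- Fall in positives: 70%. Protocol 4.3 gives about this figure for total IgG in MG0002. Carrying it over to an autoantibody, at every visit, is an assumption.
- Share positive for the antibody plotted, p: not in the documents. Range taken: 5% to 95%.
- Assay CV: not in the documents. Range taken: 10% to 40%.
- Negative samples return a numeric or imputed value: an assumption, since the SAP is silent.
- Post-Baseline samples: 7 (Weeks 5, 9, 21, 33, 45, 52 and 60, from the Schedule of Activities).

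**1. Dilution with no change in negatives.** Plotted mean = p x (-70%) + (1 - p) x 0.

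| p | Plotted mean | Positives only |
|---|---|---|
| 5% | -3.5% | -70% |
| 10% | -7% | -70% |
| 20% | -14% | -70% |
| 50% | -35% | -70% |
| 90% | -63% | -70% |
| 95% | -66.5% | -70% |

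Mean absolute change shrinks by the same factor p.

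**2. Assay noise in negatives, percentage change.** For two independent log-normal values with the same mean and CV, the expected ratio is 1 + CV². Negatives therefore show a mean percentage change of +CV²: +1%, +4%, +9% and +16% at CV 10%, 20%, 30% and 40%. With p = 10%:
- CV 10%: 0.9 x 1 - 7 = -6.1%
- CV 20%: 0.9 x 4 - 7 = -3.4%
- CV 30%: 0.9 x 9 - 7 = +1.1%
- CV 40%: 0.9 x 16 - 7 = +7.4%

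The sign reverses when 0.9 x CV² exceeds 0.07, that is CV above √0.0778, about 28%. At p = 20% and CV 40% the result is 0.8 x 16 - 14 = -1.2%, so there is no reversal. Noise of this kind does not bias the mean absolute change, because its expected difference is zero.

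**3. Maximum change.** This was read as the largest percentage reduction over the 7 samples (200,000 simulated participants). Noise alone gives negatives a mean maximum reduction of about 12%, 21% and 29% at CV 10%, 20% and 30%. At CV 20%:

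| p | All participants | Positives only |
|---|---|---|
| 10% | about -27% | about -76% |
| 50% | about -49% | about -76% |
| 90% | about -71% | about -76% |

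**4. If negatives are zero or non-numeric.** Percentage change has no valid denominator. SAP 3.1 bases continuous summaries on participants with available measurements, so these participants may drop out and the percentage dilution disappears. The n behind the curve would then fall for a reason the SAP does not state.

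**The case against.** **Undiluted by-visit figures are already planned.** This stands if the restricted summary is read antibody by antibody. A reader might take the phrase about anti-MuSK or anti-AChR positivity to mean positive for either, which would keep nearly everyone. The documents do not favor that reading. SAP 4.9, 9.1.2 and 9.1.3 use the same pairing as two subgroup levels, and an either-antibody table would almost repeat the main summary. The wording needs tightening, but the table cannot be counted as failed. It does not cover the maximum change or any figure.

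**The effect depends on laboratory reporting that cannot be seen.** This stands, and makes the dilution conditional. The SAP's silence is part of the problem.

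**The anti-AChR outputs are probably little affected.** This stands if most participants are AChR-positive. The documents give no split.

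**The plotted curve need not point the wrong way.** This stands. A reader might infer that noise would turn the anti-MuSK curve upward, but that needs both a low positive share and an assay CV for which the documents give no support.

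**These are descriptive outputs under an Other objective.** This also stands. It limits the importance of the point but does not justify a mechanism figure built on the wrong participants.

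**Conclusion.** The point holds for the maximum-change summary, the mean absolute and percentage change plots, and the combined anti-MuSK and anti-AChR figures. Inclusion of antibody-negative participants follows from the Safety Set default and the absence of any restriction; the SAP does not say it outright.

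The size is conditional. With numeric or imputed values in negatives and the borrowed 70% fall, the rarer antibody's plotted mean loses most of its size, while the commoner one loses 3.5 to 7 percentage points. With undefined percentage changes in negatives there may be no percentage dilution at all.

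A reader might infer that all reported autoantibody lowering is diluted or replaced by noise. The documents do not support that: a by-visit summary in Baseline-positive participants and participant listings are planned, and no primary or secondary conclusion is touched.

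**What to change.** In SAP 10.2.2:

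1. For each antibody, restrict the maximum-change summary, the mean-change plots and the combined figure to participants positive for that same antibody. In the combined figure, compute the IgG, MG-ADL, QMG and MG-C curves on the same participants.
2. For percentage change, also require a quantifiable MG0004 Baseline. Positivity in MG0003 does not guarantee one, because SAP 3.3 takes Baseline just before the first MG0004 dose and some participants arrive after active treatment in the lead-in study.
3. State which positivity definition applies: the MG0003-derived status of SAP 4.9, or Baseline status as in SAP 6.2 and the existing restricted summary.
4. Apply the LLOQ/2 rule of SAP 10.4 to values below quantification.
5. Reword the restricted by-visit summary as two tables: anti-AChR in AChR-positive and anti-MuSK in MuSK-positive participants.
6. Show n at each visit on every table and figure.

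The cost is a few lines of SAP text and one filter per output, with no new data. The downside is a small and possibly unstable MuSK-positive set, which the displayed n makes visible.
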